9.7.5. Local Failure

Local failure will be defined as >20% increase in the sum of the largest diameter of all targeted tumors.

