11.5.2. Efficacy Endpoints

The efficacy endpoint for this study is defined as follows: local tumor control in patients with pulmonary metastatic disease at 3, 6, 12, 24, 36, 48 and 60 months post cryoablation.

Tumor control will be determined by examining the change from baseline at follow-up visits. Post-treatment imaging including CT/MRI will be reported for baseline and follow-up visits. Tumor control will be defined by the criteria defined in Section 9.7 of this protocol.

CUC10-LNG06-04 Page 19 of 38

Patients are allowed up to 5 tumors so tumor control will be calculated on a per tumor level as well as a patient level. To be considered a success on a patient level all tumors treated during the baseline procedure must meet the tumor control criteria at that follow-up visit.

The local tumor control counts and rates will be presented along with the 95% two-sided confidence intervals for the rates. The rate at the each visit will be defined as the proportion of tumors/patients experiencing tumor control at a specific timepoint out of the number of patients who complete a follow-up visit at that timepoint.

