#### **Analysis Methods**

Patients may have up to five tumors so tumor control will be calculated on a per tumor level as well as a patient level. To be considered a success on a patient level all tumors treated during the baseline procedure must meet the tumor control criteria at that follow-up visit.

Post-treatment imaging including CT/MRI will be reported for baseline and follow-up visits. Tumor control for each time point will be determined by examining the change from baseline, and will be defined as:

Complete Response – Tumor disappearance or a  $\geq$  75% decrease in the greatest transaxial diameter ( <25% of original size).

Partial Response – A <75% but ≥30% decrease in the greatest trans-axial diameter.

**Stable Disease** – No change, allowing for a <30% decrease up to a <20% increase in the greatest trans-axial diameter.

**Local Failure** – A ≥20% increase in the greatest trans-axial diameter.

**Local Control** – Local control will be defined as the absence of local failure. Tumors in complete response, partial response and stable disease will all be in local control.

**Distant Failure** – Distant failure (e.g. metastatic disease) will be defined as the appearance of distant cancer deposits consistent with metastatic spread of cancer outside the intended treatment area.

The local tumor control counts and rates will be presented along with the 95% two-sided confidence intervals for the rates. The rate at the each visit will be defined as the proportion of tumors/patients experiencing tumor control at a specific time point out of the number of patients who complete a follow-up visit at that time point.

Efficacy analyses will be performed on the ITT population. Analysis of the PP population may be done in support of the ITT analysis. No formal statistical hypothesis testing will be performed for efficacy endpoints.

Confidential Page 3 of 9

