#### **Analysis Methods**

Point estimates and two-sided Exact 95% confidence intervals will be generated for events related to the cryoablation procedure in the following categories:

- intra-operative events
- post-operative adverse events
- · serious adverse events
- unanticipated adverse device effects

The safety analysis will be performed on the ITT population. No formal statistical hypothesis testing will be performed for safety endpoints.

Confidential Page 4 of 9

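### The per-tumor control rate is given a patient denominator, and Protocol and SAP define local failure on different units

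*SAP*

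**What the plan says.** **Two levels, one denominator.** The SAP's efficacy Analysis Methods state: "Patients may have up to five tumors so tumor control will be calculated on a per tumor level as well as a patient level". For the patient level, "all tumors treated during the baseline procedure must meet the tumor control criteria at that follow-up visit". For both levels the rate then reads: "proportion of tumors/patients experiencing tumor control at a specific time point out of the number of patients who complete a follow-up visit". Protocol 11.5.2 has the same construction: "tumors/patients experiencing tumor control at a specific timepoint out of the number of patients who complete a follow-up visit at that timepoint". Neither document gives a denominator counted in tumors.

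**Two units for failure.** Protocol 11.5.2 says: "Tumor control will be defined by the criteria defined in Section 9.7 of this protocol". Within that section, 9.7.5 defines local failure as a more than 20% "increase in the sum of the largest diameter of all targeted tumors". The SAP instead grades change in greatest trans-axial diameter, with local failure at an increase of 20% or more, and counts control by tumor: "Tumors in complete response, partial response and stable disease will all be in local control". Its list of imaging summaries also shows response and diameter for each tumor.

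**Intervals.** Both documents promise two-sided 95% intervals for the control rates without naming a method. For safety the SAP does name one: "Point estimates and two-sided Exact 95% confidence intervals will be generated for events related to the cryoablation procedure".

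**The concern.** Local control is the only efficacy endpoint, and the per-tumor rate is one of the two levels at which it is reported. If the stated rule is followed, that rate is a mean count of controlled tumors per patient presented as a percentage. A value above 100% would be noticed. A value inflated but still below 100% would not, and that is the more awkward case.

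The failure definition is a separate problem. A criterion on the sum over all targeted tumors gives one result per patient. It cannot classify a single tumor, so it supports neither the per-tumor rate nor the rule, which Protocol 11.5.2 shares with the SAP, that every treated tumor must be in control for the patient to count as a success.

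Both documents say that estimates from this study will be used to power a pivotal trial, so a misdefined rate could carry forward.

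**Working it through.** The plan derives no precision or sample-size figure for the control rate, so there is none to reproduce.

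**1. The rate as written.** Let K be patients completing the visit, T their treated tumors, Y the tumors in control, m = T/K and p = Y/T. The written per-tumor rate is Y/K = (T/K)(Y/T) = m × p. It exceeds 100% when p > 1/m. The documents give a maximum of 5 tumors per patient but no expected m, so the values of m below are assumptions. The value 1.75 is 35/20, from one earlier series in Protocol 3.2.

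| m | written rate at p = 80% | exceeds 100% when p is above |
|---|---|---|
| 1.0 | 80% | never |
| 1.1 | 88% | 91% |
| 1.37 | 110% | 73% |
| 1.75 | 140% | 57% |
| 2.0 | 160% | 50% |

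The ceiling is 500% (150 tumors in 30 patients, or 200 in 40). In the 35-tumor series 7 tumors recurred locally, leaving 28: 28/20 = 140% as written, 28/35 = 80% with a tumor denominator. Recurrence in that series is not this plan's control criterion, so this only illustrates the arithmetic.

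**2. How often 100% would be passed.** Simulation inputs, all assumed except the 40 patients: 80% control, within-patient correlation 0.3, beta-binomial model, 20,000 runs. With 55/25/12/5/3% of patients having 1 to 5 tumors (mean 1.76), the written rate exceeded 100% in 99.5% of runs. With 75/17/5/2/1% (mean 1.37) it did so in 74.6%.

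**3. The interval.** With 48 controlled tumors and 30 patients, the Wald, Wilson and Clopper-Pearson limits are all undefined. At patient level an interval exists, but the unnamed method matters at this size. For 27/30 the lower limit is 79.3% (Wald), 74.4% (Wilson) or 73.5% (Clopper-Pearson). For 30/30 it is 100% (Wald) or 88.4% (Clopper-Pearson).

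**4. Failure on the sum or on each tumor.** Take two tumors of 2.0 and 1.0 cm that become 1.0 and 1.5 cm.

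- Sum: (1.0 + 1.5)/(2.0 + 1.0) − 1 = −17%. No local failure under Protocol 9.7.5.
- Each tumor: 1.0/2.0 − 1 = −50% (partial response) and 1.5/1.0 − 1 = +50% (local failure) under the SAP.
- Result: the patient is controlled under the Protocol definition and a failure under the SAP. The SAP counts one tumor of two in control; giving both tumors the sum's status counts two of two.

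The change in the sum is the average of the tumor changes weighted by baseline diameter: (2/3)(−50%) + (1/3)(+50%) = −17%. A sum that grows by more than 20% therefore needs at least one tumor that grows by more than 20%. With the same diameters measured, the summed rule can only leave patient-level control equal or higher, never lower. With one tumor per patient the two rules agree, apart from a change of exactly 20%.

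**5. Within-patient correlation, after the denominator is corrected.** An exact 95% interval that treats tumors as independent covers as follows at correlation 0.1/0.3/0.5 (40 patients, 80% control, same simulation): 95.3/92.7/89.7% at mean 1.76 tumors and 96.1/94.7/92.9% at mean 1.37.

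For the cost in width, use half-width = 1.96 × √[p(1 − p) × D/T] with D = 1 + (m − 1) × correlation. With 30 patients, m = 1.75 (T = 52.5) and p = 0.9, it is 8.1 points at correlation 0 (D = 1), 8.7 at 0.2 (D = 1.15) and 9.5 at 0.5 (D = 1.375).

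**The case against.** The strongest reply is that the slash is shorthand. The sentence calls the rate a proportion, the same section asks for a per-tumor result, and a sensible programmer would divide tumors by tumors. That is probably the intent, and it stands as a reason to treat this as a drafting defect. It does not close the point: even as shorthand, the sentence does not say whether all treated tumors count or only those with evaluable imaging at the visit.

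Three stronger readings do not hold.

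- *A reader might infer that the study will report control above 100%.* The documents do not show this. It requires m × p > 1, cannot happen with one tumor per patient, and would be caught at first output.
- *A reader might infer that ignoring correlation seriously invalidates the per-tumor interval.* At low to moderate correlation coverage is near nominal; the clear shortfall, 89.7%, needs an assumed correlation of 0.5 and the heavier tumor mix. The documents give no correlation.
- *A reader might count the unnamed interval method as an error.* It is missing detail in a descriptive study with no efficacy test.

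The opposite overstatement also fails. It is tempting to say that the patient-level rate is untouched. Its denominator is indeed valid, but step 4 shows that the failure definition can change a patient's status.

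**Conclusion.** Two defects hold on the text of both documents.

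1. The per-tumor control rate is wrong as written. Its only stated denominator is patients, which inflates it by the mean number of tumors per patient. The size therefore depends on a quantity that the plan does not give: a factor of 1.1 turns 80% into a plausible 88%, and a factor of 1.75 turns it into 140%. The patient-level denominator gives a valid proportion.

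2. Protocol 9.7.5 and the SAP define local failure on different units. The conflict affects only patients with more than one treated tumor, apart from changes of exactly 20%. There it can change both the per-tumor and the patient-level rate, and at patient level the summed rule can only favor control.

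The interval method and the clustering of tumors within patients are secondary. Because the study is descriptive, no test or error rate is at stake. The consequence is a misdefined estimate that could be carried into the pivotal design. The point should be corrected before analysis, but it does not undermine the study.

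**What to change.** 1. **Denominators, in both documents.** Per-tumor rate = tumors treated during the baseline procedure that are in control, divided by tumors treated during the baseline procedure with evaluable imaging at that visit. Keep the rule that all tumors must be in control for a patient-level success. State the patient denominator on the same evaluable-imaging basis, and report how many patients attended without evaluable imaging. Say how a patient with only some tumors evaluable is counted. Because Protocol 7.2.4 puts treatment of the two lungs on separate days, also say whether both days belong to the baseline procedure.

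2. **Failure definition.** Reconcile Protocol 9.7.5 with the SAP so that each tumor has its own failure status.

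3. **Intervals (secondary).** At patient level, use the exact interval that the SAP already names for safety. At tumor level, name one standard interval that clusters tumors within patient, for example a patient-clustered robust interval on the logit scale, and say what is reported if every tumor is controlled. Avoid an improvised exact interval on an effective sample size that switches to the number of patients when all tumors are controlled. For 40 patients and 70 tumors, its lower limit is 91.2% at 70/70 but 92.1 to 92.3% at 69/70, so the worse result gets the better bound.

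The cost is a few sentences in each document and no new data. The downside is a modestly wider per-tumor interval, as in step 5 of the working.

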6.2. Additional Treatment

Patients may not receive additional local treatment to the index tumor(s) subjected to cryoablation while participating in the study protocol. If additional local treatment (e.g. ablation, surgery, radiation) is required, then the patient must be withdrawn from the study.

Data will be collected on any additional systemic cancer therapy the patients receive during the course of the study.

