8.1. Screening

The screening period begins after written informed consent has been obtained. The screening visit allows the investigator to assess a patient's eligibility for this study.

CUC10-LNG06-04 Page 13 of 38

b Month 1 visit may be done by telephone interview or clinic visit. Visit window +21/-7 days

Complete only if a Clinic Visit

d Months 3, 6 and 12 visit window +45 days

e Months 24, 36, 48 and 60 visit window +90 days

f CT/MRI scan with contrast for follow-up at 3 months, 6 months, 1 year then yearly per routine post treatment f/u

Week 1 imaging may be a CT, MRI or X-Ray with or without contrast

h Platelet Count, ANC and INR – within 60 days of study procedure

ⁱTo be completed before treatment starts then at 1, 3, 6, 12, 24, 36, 48 and 60 months post cryoablation

The following assessments will be completed during screening and within 6 weeks of the cryoablation procedure:

- Informed consent;
- Review inclusion/exclusion criteria;
- Patient number assigned;
- Demography;
- Targeted medical history, including comorbidities;
- ECOG:
- Karnofsky Performance Scale;
- Baseline labs (Platelet Count, ANC and INR);
- CT/MRI scan of chest with contrast to include lungs, liver, and adrenal glands;
- Tumor characteristics (See Section 5.4);
- Quality of Life assessments (SF-12);
- Current pertinent concomitant medication;
- Discontinue anticoagulation as clinically indicated;
- Assess for clinical safety of General Anesthesia (if applicable).

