8.5. Months 3, 6 and 12 - Follow-up

Patients will return 3, 6 and 12 Months (+/-45 days) post cryoablation procedure to complete the following assessments:

- ECOG:
- Karnofsky Performance Scale;
- Quality of Life assessments (SF-12);
- CT/MRI Scan, with contrast;
- Safety assessments;
- Assessment of disease progression, including retreatment;
- Assess any new cancer treatment(s).

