# **Analysis Populations**

All analyses will be performed on the Intent-to-Treat (ITT) population consisting of all subjects treated with a Galil Medical Cryoablation System and needles as the attempted treatment. A per-protocol (PP) analysis may also be done, removing subjects who did not have a complete treatment and those that did not meet the study criteria but were enrolled.

Confidential Page 2 of 9

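### Visit-by-visit local control rates lose failures that are retreated and withdrawn, so later rates overstate control if read as durable control

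*SAP*

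**What the plan says.** The efficacy endpoint is local tumor control at 3, 6, 12, 24, 36, 48 and 60 months. Under Analysis Methods in the SAP's efficacy section, control is the absence of local failure, and failure is growth of at least 20% over baseline in the greatest trans-axial diameter. The rate at each visit is taken "out of the number of patients who complete a follow-up visit at that time point". Protocol 11.5.2 has the same rule: "out of the number of patients who complete a follow-up visit at that timepoint". Several tumors per patient are allowed, "so tumor control will be calculated on a per tumor level as well as a patient level". A patient succeeds at a visit only if every treated tumor is in control at that visit.

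Protocol 6.2 says of the ablated tumors: "If additional local treatment (e.g. ablation, surgery, radiation) is required, then the patient must be withdrawn from the study". Yet Protocol 8.5 lists "Assessment of disease progression, including retreatment" among the assessments at Months 3, 6 and 12, and Protocol 8.6 repeats the item for later visits and for withdrawal.

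The SAP's population statement reads: "All analyses will be performed on the Intent-to-Treat (ITT) population consisting of all subjects treated". Its missing-data section uses whatever data dropouts have provided and gives no rule for a patient who failed earlier. A supportive Kaplan-Meier analysis covers freedom from recurrence or progression.

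**The concern.** Local failure is an obvious reason for further local treatment. If such a patient is withdrawn under Protocol 6.2, the failure counts at most at the visit that detected it. At later visits the patient is in neither numerator nor denominator. This loss is tied to the outcome and produced by a protocol rule, so it is not ordinary dropout.

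Nothing else in the efficacy analysis restores these patients. The intent-to-treat label says who is analysed, but the visit denominator then narrows that group to completers. Protocol 8.6 schedules a scan at withdrawal, but no text assigns it to a time point. No text says whether retreatment itself counts as local failure.

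What is at stake is interpretation and planning. The SAP's Sample Size Justification says estimates from this study will be used to power a pivotal study, without saying which ones. A Month 60 completer rate taken as durable control could make that planning value too high.

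**Working it through.** **Stated figures.** There is no planned control rate or power calculation to reproduce. The 30 to 40 patients are justified as clinically sufficient. The failure and withdrawal inputs below are therefore assumptions.

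**Direction.** At a given visit let *c* patients be in control, *f* failures still attend, and *x* earlier failures have been withdrawn. The plan reports c/(c+f). Keeping the withdrawn failures gives c/(c+f+x), which is smaller whenever c and x exceed zero.

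**Size, illustrative.** Let *q* be the failure risk per visit interval among controlled patients and *w* the share of failures withdrawn after the detecting visit. Failure is taken as permanent, and any other loss as unrelated to tumor status. True control at the k-th visit is S_k = (1−q)^k. Those attending are the controlled (S_k), the newly failed (q·S_(k−1)) and earlier failures not withdrawn ((1−w)(1−S_(k−1))). So:

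reported rate = S_k / [S_k + q·S_(k−1) + (1−w)(1−S_(k−1))]

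For Month 60, k = 7. With q = 0.05, S_7 = 0.6983 and S_6 = 0.7351. At w = 0.5 the denominator is 0.6983 + 0.0368 + 0.5 × 0.2649 = 0.8675, and 0.6983/0.8675 = 80.5%.

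| Share of failures withdrawn | Month 3 | Month 12 | Month 60 | Month 60 excess |
|---|---|---|---|---|
| 0 (true control) | 95.0% | 85.7% | 69.8% | 0 |
| 20% | 95.0% | 87.4% | 73.7% | 3.9 points |
| 50% | 95.0% | 90.1% | 80.5% | 10.7 points |
| 100% | 95.0% | 95.0% | 95.0% | 25.2 points |

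If every failure is withdrawn, the reported rate is flat at 95% and says nothing about durability.

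**Sensitivity to q at Month 60.** With q = 0.02, true control of 86.8% reads 88.8%, 92.1% or 98.0% at w = 20%, 50% or 100%. With q = 0.10, true control of 47.8% reads 52.8%, 62.5% or 90.0%. The excess passes 5 points only when more than about 48%, 25% or 20% of failures are withdrawn, for q = 0.02, 0.05 and 0.10 respectively.

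**Per-tumor rate.** I simulated two independent tumors per patient, with the patient-level risk still 5% per interval. True Month 60 control of 83.6% reads about 85.7%, 89.4% or 97.5% at w = 20%, 50% or 100%.

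**An apparent remedy that fails.** One could keep withdrawn failures in later denominators as failures. But controlled patients lost for ordinary reasons still drop out, so the result is biased the other way. Take 40 patients, q = 0.05, w = 5/7 (an assumption) and 15% ordinary loss per interval. At Month 60 there are 40 × 0.85^7 × 0.8108 = 10.40 completers, of whom 40 × 0.85^7 × 0.6983 = 8.95 are controlled. Failures withdrawn earlier number 40 × (5/7) × 0.05 × Σ(0.95^(j−1) × 0.85^j, j = 1 to 6) = 4.56. The rate is 8.95/(10.40 + 4.56) = 59.9%, against a true 69.8%. With 5% or 10% loss it is 67.2% or 63.9%.

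**The case against.** The strongest reply is that the plan contains no error here. Success is defined at each follow-up visit, the denominator is stated openly, the rate is never called cumulative, and there is no test or threshold. That stands. A reader might infer that the reported rates are invalid or mislabelled; the documents do not support that. The words *true* and *excess* above refer to durable control. Under the plan's visit-by-visit comparison with baseline, a tumor can return to control.

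Second, a measure that retains failures is already planned. The Kaplan-Meier analysis counts any size increase and/or contrast enhancement as an event, so growth of at least 20% recorded before withdrawal is caught. This largely stands too. What it lacks is a per-tumor version, an estimate on the endpoint's own criterion, and a rule for retreatment without growth.

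Third, a reader might infer that every local failure disappears, or that the bias is known to be large. Neither follows. Failures that are not locally retreated stay in the denominator, and Sections 8.5 and 8.6 leave it unsettled whether retreated patients leave. The series of small metastatic tumors in Protocol 3.2 reports seven patients with local recurrence and five patients with additional cryosurgery, but does not say how far they overlap, so it supplies no withdrawal share.

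Nor is retreatment hidden. The SAP summarises new treatments under Disease status, and Protocol 6.4 records reasons for withdrawal where given. Only a disposition line linking the two is missing.

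Finally, sampling error may exceed the bias. With 15% of patients lost per interval and w = 5/7, about 10 of 40 complete Month 60, and the exact 95% interval for 9/10 is 55.5% to 99.7%. That is fair, but an interval around a conditional rate does not turn it into an estimate of durability.

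**Conclusion.** The point holds, as a minor one. To the extent that local failures are retreated and withdrawn, visit rates after the detecting visit overstate durable control. The direction is certain against a measure that keeps those failures. The size is not in the documents: at an assumed 5% failure per interval, the Month 60 excess runs from 0 to 25.2 points as the withdrawn share goes from none to all. It is zero if no failure is retreated, and zero at Month 3 if the failing scan is counted there. As a description of patients still attending, the rate is sound.

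**What to change.** In SAP Analysis Methods and Protocol 11.5.2:

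1. Add time to local failure in all treated patients. The event is the earlier of growth of at least 20% on any scan from the Month 3 visit onward, withdrawal scans included, or further local treatment of an already ablated index tumor. Tabulate the two event types separately. A planned second-day treatment of other tumors is not an event. Report cumulative incidence with 95% intervals at 3, 6, 12, 24, 36, 48 and 60 months, with death as a competing event and other losses censored at last imaging. Add a per-tumor version whose intervals allow for several tumors per patient. Earlier scans are left out because the ablation zone could be measured as growth: a 5 mm margin all round turns 35 mm into 45 mm (+28.6%).
2. Keep the completer rate, labelled *conditional on follow-up at that visit*. Show beside it the number previously withdrawn for index-tumor retreatment.
3. Add a Subject Disposition row for those withdrawals.

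Do not add a visit rate that carries only withdrawn failures forward, for the reason shown in the calculation. It would also need vital status after withdrawal, which no section schedules. Do not assign only the failures from off-schedule scans to visits, since that is one-sided.

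State the day on which the Month 3 window opens. Table 1 footnote d has "Months 3, 6 and 12 visit window +45 days" and Section 8.5 has "Patients will return 3, 6 and 12 Months (+/-45 days) post cryoablation procedure", which may be no more than a lost plus-minus sign.

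The sponsor must reconcile Protocol 6.2 with Sections 8.5 and 8.6 on retreatment and withdrawal; no clinical rule is proposed here.

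The cost is wording, one added analysis at two levels and one table row, with no new visits or procedures. The sponsor should confirm that the date and target of any retreatment are recorded. The downsides are that durability may look less favourable, an extra summary with its own definition must be explained, and retreatment without 20% growth counts as an event.

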9.7.1. Local Control

Local control will be defined as the absence of local failure.

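### The local control rate is divided by patients who complete a visit, an undefined term, rather than by patients or treated tumors assessable on CT/MRI

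*SAP*

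**What the plan says.** **Denominator.** The SAP (Efficacy Endpoint Analysis, Analysis Methods) counts tumors or patients in control at a time point "out of the number of patients who complete a follow-up visit at that time point". Protocol 11.5.2 has the same rule: "out of the number of patients who complete a follow-up visit at that timepoint". Neither sentence mentions a scan.

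**Numerator.** The SAP bases it on imaging: "Tumor control for each time point will be determined by examining the change from baseline". Each SAP response category is a percentage change in greatest trans-axial diameter. Control is then described in two ways. Protocol 9.7.1 reads "Local control will be defined as the absence of local failure"; the SAP repeats this and adds "Tumors in complete response, partial response and stable disease will all be in local control". For a patient-level success, "all tumors treated during the baseline procedure must meet the tumor control criteria at that follow-up visit".

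**Visit content.** Protocol 8.5 introduces a list of seven items with "Patients will return 3, 6 and 12 Months (+/-45 days) post cryoablation procedure to complete the following assessments". The fourth item is "CT/MRI Scan, with contrast". Protocol 8.6 has the same list for Months 24 to 60, and Table 1 and Protocol 9.6 also schedule CT or MRI at every efficacy time point.

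**Missing or unreadable scans.** Protocol 9.7.2 covers two cases: a tumor judged to have gone is recorded as 0 mm, and one faintly visible but too small to measure is given 5 mm. Protocol 11.3 and the SAP's Handling of Missing Data have no rule for a scan that was not done or a tumor that cannot be assessed. The SAP's Subject Disposition section counts patients completing each visit but does not say what completion requires.

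**The concern.** The denominator refers to a visit and the numerator to a scan, and nothing in the plan ties the two together. The patients affected are those who attend (for performance status, SF-12 and safety, say) but have no scan in the window, or a scan on which a treated tumor cannot be assessed. Patients who miss the visit altogether are a different matter.

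For those attendees the analyst has to choose a reading, possibly with the data in view. With up to five tumors per patient, one unassessable tumor is enough to leave the patient-level result undetermined.

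A second fault sits in the same sentence. It covers both the per-tumor and the per-patient rate but gives only patients as the denominator, so read literally the per-tumor rate divides a count of tumors by a count of patients.

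Local control is the only efficacy endpoint. No hypothesis test depends on it, but the sample size sections of both documents say that the study's estimates will be used to power a pivotal study.

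**Working it through.** **1. Is there a figure to reproduce?** No. The 30 to 40 patients are justified on clinical grounds. The documents state no expected control rate, share of missing scans or interval width, so the inputs in step 3 are assumptions.

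**2. Readings of the denominator for an attendee without a usable scan.**

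- *Completing means attending, and control requires a response category.* The patient is in the denominator and cannot be in the numerator, so is scored as not controlled.
- *Completing means attending, and control is only the absence of failure.* No failure has been shown, so the patient is scored as controlled. This takes one sentence apart from its neighbors, which require a change from baseline.
- *Completing means finishing all listed assessments.* The patient is excluded. So is a patient with a readable scan and a missing SF-12, although that patient's tumor outcome is known.

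**3. Size of the difference.** Let V be attendees, u those without an assessable scan, and c those controlled among the V − u who are assessable.

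- Assessable only: c/(V − u)
- Unassessed as not controlled: c/V = [c/(V − u)] × (1 − u/V)
- Unassessed as controlled: (c + u)/V
- Gap between the last two: u/V, whatever c is

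V is set at the planned 30 or 40. The assumed values of u run from none to 20% of attendees, with about 80% or 90% control among those assessed.

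| V | u | c | c/(V − u) | c/V | (c + u)/V | Gap (points) |
|---|---|---|---|---|---|---|
| 30 | 0 | 27 | 27/30 = 90.0% | 90.0% | 90.0% | 0 |
| 30 | 2 | 25 | 25/28 = 89.3% | 25/30 = 83.3% | 27/30 = 90.0% | 6.7 |
| 30 | 3 | 22 | 22/27 = 81.5% | 22/30 = 73.3% | 25/30 = 83.3% | 10.0 |
| 30 | 3 | 24 | 24/27 = 88.9% | 24/30 = 80.0% | 27/30 = 90.0% | 10.0 |
| 30 | 6 | 22 | 22/24 = 91.7% | 22/30 = 73.3% | 28/30 = 93.3% | 20.0 |
| 40 | 4 | 32 | 32/36 = 88.9% | 32/40 = 80.0% | 36/40 = 90.0% | 10.0 |
| 40 | 8 | 29 | 29/32 = 90.6% | 29/40 = 72.5% | 37/40 = 92.5% | 20.0 |

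For the third row, Clopper-Pearson 95% limits are 61.9 to 93.7% for 22/27, 54.1 to 87.7% for 22/30 and 65.3 to 94.4% for 25/30. Exact limits are an assumption here, because the SAP names them only for safety.

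**4. Tumors over patients.** Read literally, the per-tumor rate is (share of treated tumors controlled) × (treated tumors per patient). It exceeds 100% whenever controlled tumors outnumber patients. For scale, Protocol 3.2 describes a metastasis series with 35 tumors in 20 patients, or 1.75 per patient. If 28 of those 35 were controlled (assumed), the literal rule gives 28/20 = 140% and the tumor denominator gives 28/35 = 80%. A binomial interval cannot be formed for 28 out of 20.

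**5. Partly imaged patients.** One failed tumor settles a patient-level failure, but controlled visible tumors do not settle a success while another tumor is unseen. Suppose that in the third row the 3 unassessed patients are partly imaged and 1 has a visible failure. Admitting only that patient to the main rate gives 22/28 = 78.6% instead of 22/27 = 81.5%. Entry would then depend on outcome and could only lower the rate.

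**The case against.** The best defense is that the scan belongs to the visit. Protocol 8.5 and 8.6 list CT/MRI among the assessments patients return to complete, so an unscanned patient has not completed the visit and is outside the denominator, much as the fix would have it. This is a fair reading. It also defeats a stronger claim that a reader might infer, namely that the plan scores unscanned patients as not controlled or as controlled. No passage says so. But the defense does not fully repair the rule: it removes patients with readable scans who lack some other item, and it does not cover a scan that was done but on which a tumor cannot be assessed.

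Three further objections stand in part:

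- The controlled-by-default reading is strained. The SAP requires a change from baseline to be examined, and without a scan there is none. It serves as an upper extreme, not a likely analysis.
- Protocol 9.7.2 already handles vanished and faint tumors, so the gap is limited to absent scans and tumors that cannot be assessed for other reasons.
- The share of missing scans is assumed and may be zero. The illustrative intervals overlap widely. The documents also give no basis for saying that completeness will differ across the seven time points.

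On the per-tumor rate, an analyst would probably use a tumor denominator without being told. That is likely, but it is not what either document says.

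The SAP will also report control counts, visit completion and per-tumor response. A careful reader could detect part of the problem from these, but they do not fix the rate in advance.

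**Conclusion.** The concern holds as a fault in the specification of the rate. The stated denominator uses an undefined term that does not match how control is determined, no rule covers an attendee without an assessable scan, and the per-tumor rate has the wrong unit below the line. It does not hold as a finding that the plan prescribes a misclassification.

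The spread between the extreme codings is u/V: nil with complete imaging, 10 points at 3 of 30, and 20 points at 6 of 30. These shares are assumptions. Only under the lower coding does the rate shrink by the factor 1 − u/V; under the upper coding it can rise, as from 81.5% to 83.3%. The tumors-over-patients fault needs no assumption about missing scans, only more controlled tumors than patients.

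Because the study is descriptive, no test result is at risk. The correction is worth making because the estimate is intended for the design of a pivotal study.

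**What to change.** Change the sentence in both the SAP's efficacy Analysis Methods and Protocol 11.5.2, so that at each time point:

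- the per-tumor rate is divided by treated tumors assessable on CT/MRI in the visit window, with the 0 mm and 5 mm conventions of Protocol 9.7.2 counting as assessable;
- the patient-level rate is divided by patients with all treated tumors assessable on CT/MRI in that window;
- partly imaged patients are left out of the main patient-level rate whatever their visible tumors show, are reported separately, and enter the sensitivity range;
- the number who attended without an assessable scan is shown beside each rate, with the rates under the two extreme assignments.

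In the sensitivity range, a partly imaged patient with a visible failure should count as not controlled at both ends. In the example of step 5 the range is then 22/30 = 73.3% to 24/30 = 80.0%, which lies below the main rate of 81.5%. This shows why such patients must be reported and not just dropped.

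The cost is one sentence in each document (a written amendment for the protocol) and a few extra columns in the table. No new data are needed. The denominator will be slightly smaller at some visits, and the main rate then describes assessable patients only, which is the reason for showing the range.
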